- 2. Current or prior use of immunosuppressive medication within 14 days before the first dose of study drug, with the exceptions of intranasal and inhaled corticosteroids or systemic corticosteroids at physiological doses, which are not to exceed 10 mg/day of prednisone, or an equivalent corticosteroid. Systemic steroid administration required to manage toxicities arising from radiation therapy delivered as part of the chemoradiation therapy for locally advanced NSCLC is allowed.
- 3. Prior exposure to any anti-PD-1 or anti-PD-L1 antibody including durvalumab.
- 4. For NSCLC cohort only:
 - a. Mixed small cell and non-small cell lung cancer histology
 - b. Any unresolved toxicity CTCAE > Grade 2 from the prior chemoradiation therapy.
 - c. Patients with ≥Grade 2 pneumonitis from prior chemoradiation therapy

5. Active or prior documented autoimmune disease within the past 2 years, inflammatory bowel disease (eg, Crohn's disease, ulcerative colitis), primary immunodeficiency, organ transplant that requires therapeutic immunosuppression, hypersensitivity to study drug or any excipient, leptomeningeal carcinomatosis, tuberculosis.

NOTE: Patients with vitiligo, Grave's disease, or psoriasis not requiring systemic treatment (within the past 2 years) are not excluded.

- 6. Female patients who are pregnant, breast-feeding or male or female patients of reproductive potential who are not employing an effective method of birth control
- 7. Any condition that, in the opinion of the investigator, would interfere with evaluation of the study drug or interpretation of patient safety or study results.

Study Drug, dosage and mode of administration

The recommended dose of Durvalumab is 10 mg/kg administered as an intravenous infusion over 60 minutes every 2 weeks, until disease progression or unacceptable toxicity. Dose escalation or reduction is not recommended. Dose withholding, or discontinuation may be required based on individual safety and tolerability.

Durvalumab will be supplied as either 500 mg (500mg/10mL) or 120 mg (120 mg/2.4mL) single-dose vial and does not contain any preservatives, aseptic technique must be observed. Administer infusion solution intravenously over 60 minutes through an intravenous line containing a sterile, low-protein binding 0.2 or 0.22 micron in-line filter.

Duration of treatment

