Data will be summarized using descriptive statistics. Continuous variables will be summarized using the number of observations, mean, SD, median, and range as appropriate. Categorical values will be summarized using the number of observations and percentages as appropriate.

The safety analysis population will include all patients who sign the ICF and receive at least one dose of durvalumab.

Adverse Events (both in terms of MedDRA preferred terms and CTCAE grade) will be listed individually by patient. Any AE occurring before treatment with durvalumab will be included in the data listings but will not be included in the summary tables of AEs.

[figure not shown]
Any AE occurring within 90 days of discontinuation of investigational product (ie, the last dose of durvalumab) will be included in the AE summaries. Any events in this period that occur after a patient has received further therapy for cancer (following discontinuation of durvalumab) will be flagged in the data listings.

The study is designed in accordance with the Health Authority requirements in India. It is intended to provide information regarding the safety profile for patients in India and will contribute additional information to the overall safety profile of durvalumab. Due to the small sample size, this study should not be directly compared to the data from any other country.

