5.2 Exclusion criteria

- 1. Concurrent enrolment in another clinical study, unless it is an observational (non-interventional) clinical study or the follow-up period of an interventional study
- 2. Current or prior use of immunosuppressive medication within 14 days before the first dose of study drug, with the exceptions of intranasal and inhaled corticosteroids or systemic corticosteroids at physiological doses, which are not to exceed 10 mg/day of prednisone, or an equivalent corticosteroid. Systemic steroid administration required to manage toxicities arising from radiation therapy delivered as part of the chemoradiation therapy for locally advanced NSCLC is allowed.
- 3. Prior exposure to any anti-PD-1 or anti-PD-L1 antibody including durvalumab.
- 4. For NSCLC cohort only:
 - a. Mixed small cell and non-small cell lung cancer histology
 - b. Any unresolved toxicity CTCAE >Grade 2 from the prior chemoradiation therapy.
 - c. Patients with ≥Grade 2 pneumonitis from prior chemoradiation therapy

5. Active or prior documented autoimmune disease within the past 2 years, inflammatory bowel disease (eg, Crohn's disease, ulcerative colitis), primary immunodeficiency, organ transplant that requires therapeutic immunosuppression, hypersensitivity to study drug or any excipient, leptomeningeal carcinomatosis, tuberculosis.

NOTE: Patients with vitiligo, Grave's disease, or psoriasis not requiring systemic treatment (within the past 2 years) are not excluded.

- 6. Female patients who are pregnant, breast-feeding or male or female patients of reproductive potential who are not employing an effective method of birth control
- 7. Any condition that, in the opinion of the investigator, would interfere with evaluation of the study drug or interpretation of patient safety or study results.

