8.2.3 Follow-up of AEs and SAEs

During the course of the study all AEs and SAEs should be proactively followed up for each patient. Every effort should be made to obtain a resolution for all events, even if the events continue after discontinuation/study completion.

Any AEs that are unresolved at the patient's last visit in the study are followed up by the investigator for as long as medically indicated, but without further recording in the eCRF.

AstraZeneca retains the right to request additional information for any patient with ongoing AE(s)/SAE(s) at the end of the study, if judged necessary. Adverse event data collection

'The following variables will be collect for each AE;

- AE (verbatim)
- The date and time when the AE started and stopped
- CTCAE grade 3 or more /Whether the AE is serious or not
- Investigator causality rating against the Investigational Product(s) (yes or no)
- Action taken with regard to Investigational Product(s)
- Select the appropriate as required: AE caused patient's withdrawal from study (yes or no)
- Outcome.

In addition, the following variables will be collected for SAEs:

- Date AE met criteria for serious AE
- Date Investigator became aware of serious AE
- AE is serious due to
- Date of hospitalisation
- Date of discharge
- Probable cause of death
- Date of death
- Autopsy performed
- Causality assessment in relation to Study procedure(s)
- Causality assessment to other medication'

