Appendix B Adverse event definitions and additional safety information

B 1 **Definition of adverse events**

An adverse event is the development of any untoward medical occurrence in a patient or clinical study patient administered a medicinal product and which does not necessarily have a causal relationship with this treatment. An AE can therefore be any unfavourable and unintended sign (e.g. an abnormal laboratory finding), symptom (for example nausea, chest pain), or disease temporally associated with the use of a medicinal product, whether or not considered related to the medicinal product.

The term AE is used to include both serious and non-serious AEs and can include a deterioration of a pre-existing medical occurrence. An AE may occur at any time, including run-in or washout periods, even if no Study treatment has been administered.

B 2 Definitions of serious adverse event

A serious adverse event is an AE occurring during any study phase (i.e., run-in, treatment, washout, follow-up), that fulfils one or more of the following criteria:

- Results in death
- Is immediately life-threatening
- Requires in- patient hospitalisation or prolongation of existing hospitalisation
- Results in persistent or significant disability or incapacity.
- Is a congenital abnormality or birth defect
- Is an important medical event that may jeopardise the patient or may require medical treatment to prevent one of the outcomes listed above.

B3 Life threatening

'Life-threatening' means that the patient was at immediate risk of death from the AE as it occurred or it is suspected that use or continued use of the product would result in the patient's death. 'Life-threatening' does not mean that had an AE occurred in a more severe form it might have caused death (e.g., hepatitis that resolved without hepatic failure).

B4 Hospitalisation

Outpatient treatment in an emergency room is not in itself a serious AE, although the reasons for it may be (e.g., bronchospasm, laryngeal oedema). Hospital admissions and/or surgical operations planned before or during a study are not considered AEs if the illness or disease existed before the patient was enrolled in the study, provided that it did not deteriorate in an unexpected way during the study.

B 5 Important medical event or medical treatment

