4 = Completely disabled. Cannot carry on any self-care. Totally confined to bed or chair	xx (xx.xx)
5 = Dead	xx (xx.xx)
Patients performance grade changed, since last visit	
Yes	xx (xx.xx)
No	xx (xx.xx)

- The Capital "N" in the column header represents the total number of patients in Safety Analysis Set.
- The small "n" in summary statistic represents the total number of patients in the row category.
- Percentages are based on total number of patients in Safety Analysis Set.
- Programmer Note: Visit x- Visit 2 up to Visit 13.
- Source: Listing 16.1.10
- Table Name: xxxxx

Document Title:	Document ID:	BP04-01
Statistical Analysis Plan	Version Number:	
Statistical Analysis Plan	Effective Date:	

Table 14.2.1.1 Adverse Events (Safety Analysis Set)

	Durvalumab
	(N=xxx)
	n (%) E
Any Adverse Event	xx (xx.xx) xx
Any Serious Adverse Event	xx (xx.xx) xx
Any Treatment Emergent Adverse Event	xx (xx.xx) xx
Any Serious Treatment Emergent Adverse Event	xx (xx.xx) xx
Treatment Emergent Adverse Event related to IMP	xx (xx.xx) xx
Treatment Emergent Adverse Event leading to IMP discontinuation	xx (xx.xx) xx
Treatment Emergent Adverse Event leading to Death	xx (xx.xx) xx

- The capital "N" in the column header represents the total number of patients in Safety Analysis Set.
- The small "n' in summary represents the number of patients in row category.
- TEAE are those adverse events which occurred after first dose of study medication.
- Note: Adverse events were coded using MedDRA version xx.x
- If a Patient has multiple occurrences of an AE, the Patient is presented only once in the respective patient count column (n)
 for the corresponding AE. Events are counted each time in the event (E)
- Source: Listing 16.3.1.1 and Listing 16.3.1.2

Document Title:	Document ID:	BP04-01
Statistical Analysis Plan	Version Number:	3.1 25-Nov-2021
Statistical Analysis Plan	Effective Date:	

Table 14.2.1.2 Summary of Adverse Event (Safety Analysis Set)

	Durvalumab (N=xxx) n (%) E
Any Adverse Event reported	xx (xx.xx) xx
Severity as per CTCAE grade	
Mild	xx (xx.xx) xx
Moderate	xx (xx.xx) xx
Severe	xx (xx.xx) xx
Life Threatening	xx (xx.xx) xx
Death	xx (xx.xx) xx
Action Taken to Study Drug	
No Change in IP	xx (xx.xx) xx
IP Temporarily Interrupted	xx (xx.xx) xx
IP Permanently Discontinued	xx (xx.xx) xx
Other	xx (xx.xx) xx
Treatment Given	
Yes	xx (xx.xx) xx
No	xx (xx.xx) xx
Relationship with Study Drug	. ,
Related	xx (xx.xx) xx
Not Related	xx (xx.xx) xx
Outcome	
Resolved	xx (xx.xx) xx

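### The TEAE rule has no worsening clause, so a pre-dose AE that worsens on durvalumab, and is updated under its old start date, may be left out of the by-term tables

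*SAP*

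**What the plan says.** The SAP text has no section defining a TEAE. The only definition is a footnote to the mock shell for Table 14.2.1.1: "TEAE are those adverse events which occurred after first dose of study medication". It mentions neither a baseline grade nor worsening. The statistical analysis part of the protocol synopsis adds: "Any AE occurring before treatment with durvalumab will be included in the data listings but will not be included in the summary tables".

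Some residual toxicity from chemoradiation is allowed at entry. Exclusion 4b removes only "Any unresolved toxicity CTCAE >Grade 2 from the prior chemoradiation therapy" and 4c removes "Patients with ≥Grade 2 pneumonitis from prior chemoradiation therapy". Grade 1 pneumonitis and other unresolved toxicity of Grade 1 or 2 may therefore be present on Day 1.

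Protocol section 8.2.2 starts AE collection at consent. Section 8.2.3 lists what is recorded for each AE, including "The date and time when the AE started and stopped". It lists no date of grade change. For SAEs it does collect the date on which the event became serious. Appendix B 1 says that an AE "can include a deterioration of a pre-existing medical occurrence".

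**The concern.** Safety is the trial's only objective, and events resembling pneumonitis or interstitial lung disease are named in the primary endpoint. Protocol section 4.2 says that radiation pneumonitis is common after lung irradiation and looks much like pneumonitis on durvalumab. Worsening of a mild event that was already present is therefore foreseeable.

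An onset-only rule handles that worsening according to how the site enters it. A new record gets a post-dose start date and counts as a TEAE. An updated record keeps its pre-dose start date and does not. Neither document says which to do, so the same clinical course can be counted for one patient and omitted for another. Any omission lowers the reported frequency.

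**Working it through.** **1. The plan's own figure.** The SAP's sample size is a precision calculation: n = 1.96² × 0.31 × 0.69 / 0.10² = 82.17, rounded up to 83 as stated. The half-width at n = 83 is 1.96 × √(0.31 × 0.69 / 83) = 9.95 points, and at the planned 100 patients it is 9.06 points. The TEAE definition does not enter this calculation, so changing it leaves the sample size as it is.

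**2. Tracing one event through the shells.** Take a Grade 1 pneumonitis recorded as an AE after consent and before Day 1, which reaches a higher grade or becomes serious after dosing.

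| Output | Site opens a new record | Site updates the old record |
|---|---|---|
| Start date of the worsened event | post-dose | pre-dose |
| Table 14.2.1.1, all-AE row (and all-SAE row if serious) | counted | counted |
| Table 14.2.1.1, TEAE rows | counted | may be omitted |
| Table 14.2.1.2 (grade, seriousness, outcome) | counted | probably counted; scope unclear |
| Tables 14.2.1.3 to 14.2.1.10 (by preferred term), where the event qualifies | counted | may be omitted |
| Listings 16.3.1.2 and 16.3.1.3 | shown | shown |

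The scope of Table 14.2.1.2 is unclear because its top row covers all reported AEs while its footnote defines E as the number of TEAEs. Tables 14.2.1.3 to 14.2.1.10 are all limited to TEAEs. The SAP has no shell for AEs of special interest or for pneumonitis, so these are the only AE summaries in which pneumonitis can be identified.

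**3. Can the analyst recover the worsening from the planned data?** For a change to serious, yes: section 8.2.3 collects the date, though the TEAE rule does not use it. For a rise in grade without seriousness, no: Listing 16.3.1.2 shows one start, one stop and one grade per record.

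**4. Size.** The documents do not say how many patients would be affected. With 100 patients in the safety set, each omitted patient lowers a preferred-term row by 1/100 = 1 percentage point. As an illustration, start from the 33.9% pneumonitis rate that protocol section 4.2 quotes for durvalumab in PACIFIC, taken as 34 of 100. Intervals are exact (Clopper-Pearson) 95%.

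| Patients omitted (assumed) | Reported rate | 95% interval |
|---|---|---|
| 0 | 34% | 24.8 to 44.2 |
| 1 | 33% | 23.9 to 43.1 |
| 3 | 31% | 22.1 to 41.0 |
| 5 | 29% | 20.4 to 38.9 |
| 10 | 24% | 16.0 to 33.6 |

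In terms of share, if 20% of cases were lost the fall would be 33.9 × 0.20 = 6.8 points, inside the 9.06-point half-width. At 30% it would be 10.2 points, outside it. Neither share has support in the documents. The starting rate is itself only a guide: onset in PACIFIC ranged up to 406 days, against about 230 days of observation here.

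**The case against.** **Most residual toxicity takes another route.** Chemoradiation toxicity usually predates consent. The schedule of activities takes medical history at Visit 1, and Listing 16.1.3 holds it with start date and ongoing status. If it worsens on drug, Appendix B 1 allows the deterioration to be an AE, and section 8.2.6 makes aggravated examination findings reportable. Such an AE would normally start after dosing and count as a TEAE. This stands, and it narrows the gap to AEs recorded between consent and Day 1. That window is short (Days -7 to 0), and the AE row of the schedule only begins at Visit 2. The window is not empty, however: section 8.2.2 collects AEs from consent, and Listing 16.3.1.1 asks about AEs since screening.

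**The footnote could be read generously.** A deterioration after dosing is arguably itself an event that occurred after dosing. The wording permits that reading but does not require it, and an updated record gives the programmer only a pre-dose start date.

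**The eCRF completion guide may settle the matter.** It may, but it is not among the documents, and the SAP rule does not refer to it.

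**Stronger readings.** A reader might infer that any patient who enters with unresolved toxicity is at risk of dropping out of the severity and serious-event results. The documents do not support that, given the medical-history route, the all-AE and all-SAE rows of Table 14.2.1.1, and the listings. A reader might also take the 3.4% Grade 3 pneumonitis rate in section 4.2 and conclude that losing one or two cases would remove much of the severe pneumonitis. That presupposes the loss. Nothing in the documents says what share of Grade 3 cases begin as pre-dose AE records, so no Grade 3 loss can be stated. The median onset of 55 days in section 4.2 suggests that many cases start well after Day 1 and are unaffected.

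**Conclusion.** The concern holds in a narrow form. Applied as an onset rule, the TEAE definition together with the synopsis rule may omit a pre-dose AE that worsens or becomes serious on durvalumab. This requires that the event was recorded as an AE between consent and Day 1, and that the site updated the record instead of entering a new one. What may be lost is the event's place in the TEAE rows and the by-preferred-term tables. Overall AE and SAE counts and the listings keep it.

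The number of patients is unknown and probably small. The direction is certain: any omission lowers the count, by 1 point per patient at N=100. The point is still worth correcting because the affected tables are the only AE summaries that show a named component of the primary endpoint, and the correction is cheap.

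**What to change.** - **SAP:** define a TEAE in the text as an AE with onset, or with an increase in CTCAE grade or a change to serious, on or after the first dose. State which pre-dose grade is the reference. The change to serious can be applied with the date already collected under section 8.2.3.
- **Protocol section 8.2.3 or the eCRF guide:** require post-dose worsening of a pre-dose AE, or of a medical-history condition, to be entered as a new AE with the date of worsening as its onset. Without this, the grade part of the definition cannot be programmed.
- **Protocol synopsis:** reword the rule on pre-dose AEs so that only those that do not worsen stay out of the TEAE summaries. This also removes the conflict with the all-AE rows of Table 14.2.1.1. State at the same time whether Table 14.2.1.2 covers all AEs or only TEAEs.

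The cost is a few sentences, minor data entry, and slightly higher AE counts. Sample size and visits do not change. It should be done before database lock, while sites can still supply worsening dates.

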This is a Phase IV, open-label, single arm, multi-center, prospective study to be conducted in India. Two cohorts of patients will be included in the current study patients with locally advanced, unresectable NSCLC whose disease has not progressed following platinum-based chemoradiation therapy (N= 100). Potential patients will undergo eligibility determination within 7 days prior to first dose. Patients who meet the protocol-defined inclusion/exclusion criteria will be prospectively enrolled in a sequential manner at 10 centres in India. All enrolled patients will be treated with durvalumab administered intravenously over 60 minutes at 10 mg/kg every 2 weeks. The treatment period for this study is 20 weeks, which corresponds to 10 doses of study drug administration. Treatment will continue as long as clinical benefit is observed for a maximum of 20 weeks or either of the criteria defined in section 7 are met, whichever is earlier. Patients who are observed to continue to receive clinical benefit from durvalumab at end of Week 20 (as defined in SoA) will continue treatment in post-trial phase (defined in section 6.7). Any patient who discontinues treatment with durvalumab before end of Week 20 on study will be followed for 90 days after discontinuation of study drug or until the start of alternate treatment intervention, whichever is earlier.

Safety will be evaluated throughout the evaluation phase and during the follow up of patients who discontinue treatment before end of Week 20 by physical exams including vital signs, AE/SAE monitoring, laboratory evaluations and recording of concomitant medications.

Screening Phase (Visit 1)

Patients, or their legally acceptable representative, will provide written informed consent before any trial-specific procedures are performed. During the Screening Phase, eligibility criteria will be reviewed and a complete clinical evaluation will be performed as specified in the Time and Event Schedule. Screening procedures will be performed 7 days before first dose (week 0, day 1). All baseline disease characteristics will be captured based evaluation performed as a part of routine clinical practice. The documented tests that are required before consideration of patient for durvalumab treatment based on the local prescribing information by investigator must have been performed 28 days before first dose (week 0, Day 1).

Evaluation Phase (Visit 2 To 11)

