8.2.2 Time period and frequency for collecting AE and SAE information

Adverse events and SAEs will be collected from time of signature of informed consent, throughout the treatment period (20 weeks) and including the follow-up period (90 days after the last dose of study drug) in patients who discontinue before 20 weeks.

If a patient discontinues from study drug for reasons other than disease progression, drug-related SAEs must be captured until the patient is initiated on an alternate intervention or upto 90 days whichever is earlier.

All SAEs will be recorded and reported to the sponsor or designee within 24 hours, as indicated in Appendix B. The investigator will submit any updated SAE data to the sponsor within 24 hours of it being available.

Investigators are not obligated to actively seek AE or SAE in former study patients. However, if the investigator learns of any SAE, including a death, at any time after a patient's last visit and he/she considers the event to be reasonably related to the Study treatment or study participation, the investigator may notify the sponsor.

The method of recording, evaluating, and assessing causality of AE and SAE and the procedures for completing and transmitting SAE reports are provided in Appendix B.

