1. INTRODUCTION

The purpose of this document is to provide a description of the statistical methods and procedures to be implemented for the analysis of data from D133HC00003 study. This document is based on protocol version 4.1 Dated 12-Oct-2022.

Document Title:	Document ID:	BP04-01
Statistical Analysis Dlan	Version Number:	3.1
Statistical Analysis Plan	Effective Date:	25-Nov-2021

The statistical planning and conduct of analysis of the data from this study will follow the principles defined in relevant ICH-E9 guidelines. Any change from the planned analysis as described in the protocol, are detailed here, and any differences described here supersede the analysis as presented in the protocol.

2. Study Objective and Design

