Recovered/ Resolved with Sequelae	xx (xx.xx) xx
Recovering/ Resolving	xx (xx.xx) xx
Not Recovered/ Not Resolved	xx (xx.xx) xx
Fatal/ result in death	xx (xx.xx) xx
Unknown	xx (xx.xx) xx
Serious Adverse Event	
Yes	xx (xx.xx) xx
No	xx (xx.xx) xx
Seriousness Criteria	,
Death	xx (xx.xx) xx
Life-threatening	xx (xx.xx) xx
Inpatient hospitalization or prolongation of existing hospitalization	xx (xx.xx) xx
Proprietary and Confidential Document	Page 29 of 77

Document Title:	Document ID:	BP04-01
Sandindinal Amelusia Plan	Version Number:	3.1
Statistical Analysis Plan	Effective Date:	25-Nov-2021

Persistent or significant disability/ incapacity	xx (xx.xx) xx
Congenital anomaly/Birth Defect	xx (xx.xx) xx
Important medical events	xx (xx.xx) xx
Therapy Discontinued	
Yes	xx (xx.xx) xx
No	xx (xx.xx) xx

- The Capital "N" in the column header represents the total number Safety Analysis Set.
- The small "n" represents the total number of patients in the row category.
- All Percentages rows are based on number of Safety Analysis Set.
- TEAE = treatment-emergent adverse event; E = number of TEAE
- All Percentages are based on the total number of Safety Analysis Set.
- Source: Listing 16.3.1.1 and Listing 16.3.1.2

Table 14.2.1.3 Summary of Treatment Emergent Adverse Events by System Organ Class and Preferred Term (Safety Analysis Set)

	Durvalumab (N=xxx)
	n (%) E
Any TEAE	xx (xx.xx) xx
System Organ Class 1	xx (xx.xx) xx
Preferred Term 1	xx (xx.xx) xx
Preferred Term 2	xx (xx.xx) xx
System Organ Class 2	xx (xx.xx) xx
Preferred Term 1	xx (xx.xx) xx
Preferred Term 2	xx (xx.xx) xx

- TEAE = treatment-emergent adverse event; N = number of Patients in the Safety Analysis Set; n = number of Patients with TEAE; E = number of TEAE
- All Percentages are based on the number of patients in Safety Analysis Set.
- System Organ Class and Preferred term are coded using MedDRA version xx.x
- System Organ classes and preferred term are sorted by descending frequency. Preferred terms are sorted by descending frequency within system organ class.
- Source: Listing 16.3.1.1 and Listing 16.3.1.2

Document Title:	Document ID:	BP04-01
Statistical Applicate Plan	Version Number:	per: 3.1
Statistical Analysis Plan	Effective Date:	25-Nov-2021

Table 14.2.1.4 Summary of Serious Treatment Emergent Adverse Events by System Organ Class and Preferred Term (Safety Analysis Set)

	Durvalumab (N=xxx)
	n (%) E
Any Serious TEAE	xx (xx.xx) xx
System Organ Class 1	xx (xx.xx) xx
Preferred Term 1	xx (xx.xx) xx

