xxxxx	XXXXXXXXXXX	XXXX	XXXX	DDMMYYYY- Ongoing	xx	xxx	xx (xx)	xxxx	xxx

Document Title:	Document ID:	BP04-01
Statistical Analysis Plan	Version Number:	3.1
	Effective Date:	25-Nov-2021

Listing 16.1.9.1 Listing of Patient Radiation Treatment

Unique	Clinical Stage of	Pathological Staging of	Pathological Staging	Histology of	Technique of	Dose of	Chemotherapy	If	No. Of
Patient ID	NSCLC	NSCLC done	of NSCLC	Tumor	Radiation	Radiation	given	Yes	Cycles
xxxxx	xxx	Yes/No	XXX	XXX	xxx	XXX	Yes/No	XXX	xxx
xxxxx	xxx	Yes/No	XXX	XXX	xxx	xxx	Yes/No	XXX	xxx
XXXXX	XXX	Yes/No	XXX	XXX	XXX	XXX	Yes/No	XXX	xxx
XXXXX	xxx	Yes/No	XXX	XXX	xxx	XXX	Yes/No	XXX	xxx
xxxxx	xxx	Yes/No	XXX	Xxx	Xxx	Xxx	Yes/No	Xxx	Xxx

Document Title:	Document ID:	BP04-01	
Statistical Analysis Plan	Version Number:	3.1	
	Effective Date:	25-Nov-2021	

Listing 16.1.9.2 Listing of Patient Radiation Treatment

Unique Patient	Type of	Chemo	No. of	Days of CRT	Performance status at time of
ID	Chemotherapy	regime	Cycles		initiation of CRT
xxxxxx	xxx	XXX	XXX	xxx	xxx
XXXXXX	xxx	XXX	XXX	xxx	XXX
XXXXXX	XXX	XXX	XXX	xxx	XXX
XXXXXX	XXX	XXX	XXX	xxx	XXX
XXXXXX	XXX	XXX	XXX	XXX	XXX

Document Title:	Document ID:	BP04-01
Statistical Analysis Plan	Version Number:	3.1
	Effective Date:	25-Nov-2021

Listing 16.1.10 Listing of Patient WHO Performance status

Unique Patient ID	Visit	Туре	WHO Performance Grade	If there any changes in performance grade since last visit
xxxxxx	xxx	XXX	xxx	Yes/No
XXXXXX	XXX	XXX	xxx	Yes/No
XXXXXX	XXX	XXX	xxx	Yes/No
XXXXXX	XXX	XXX	xxx	Yes/No
XXXXXX	XXX	XXX	xxx	Yes/No

Document Title:	Document ID:	BP04-01
Statistical Analysis Plan	Version Number:	3.1
	Effective Date:	25-Nov-2021

Listing 16.3.1.1 Listing of Patient Adverse Event

Unique Patient	Visit	Patient have any Adverse	Patient have any Adverse
ID		Event since screening visit	Event since last visit
xxxxxx	XXX	Yes/No	Yes/No
xxxxxx	xxx	Yes/No	Yes/No
xxxxxx	XXX	Yes/No	Yes/No
xxxxxx	XXX	Yes/No	Yes/No
XXXXXX	XXX	Yes/No	Yes/No

Document Title:	Document ID:	BP04-01
Statistical Analysis Plan	Version Number:	3.1
	Effective Date:	25-Nov-2021

Listing 16.3.1.2 Listing of Patient Adverse Event

Unique	Adverse	AE No.	Adverse Event	System organ	Preferred	Start Date and time	Stop Date and time	Severity as per	Action taken
Patient	Event		Term	class	Term			CTCAE grade	
ID									
xxxxxx	Yes/No	XXX	XXX	xxx	XXX	DD-MMM-YYYY/HH:MM	DD-MMM-YYYY/HH:MM	xx	xxx
XXXXXX	Yes/No	XXX	XXX	xxx	XXX	DD-MMM-YYYY/HH:MM	DD-MMM-YYYY/HH:MM	Xx	xxx

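### SAP Table 14.2.1.1 puts pre-dose AEs into a summary table against the protocol's rule, Table 14.2.1.2 is unclear on scope, and no AE row is named as the primary estimate

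*SAP*

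**What the plan says.** **Collection.** Protocol 8.2.2 states: "Adverse events and SAEs will be collected from time of signature of informed consent". Consent is taken at the screening visit, and the synopsis says: "Potential patients will undergo eligibility determination within 7 days prior to first dose". AEs can therefore be recorded for up to 7 days before dosing. SAP Listing 16.3.1.1, a named source for both tables discussed here, has a column asking about any AE with the wording "Event since screening visit".

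**Protocol rule.** Under Statistical Analysis, the synopsis says that an AE before treatment with durvalumab "will be included in the data listings but will not be included in the summary tables of AEs".

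**SAP Table 14.2.1.1.** The first two rows are any AE and any SAE. Separate rows for any TEAE and any serious TEAE follow. The footnote reads: "TEAE are those adverse events which occurred after first dose of study medication".

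**SAP Table 14.2.1.2.** The title and rows carry no treatment-emergent restriction, and the top row is "Any Adverse Event reported". The footnote reads: "TEAE = treatment-emergent adverse event; E = number of TEAE".

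**Primary endpoint.** SAP 6.1.1 and 6.3.1 list AEs, SAEs, AEs of special interest and on-study deaths in the Safety Analysis Set. Neither section says treatment-emergent.

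**Precedence.** The SAP introduction says that changes from the protocol's planned analysis are detailed in the SAP and that "any differences described here supersede the analysis as presented in the protocol". This change is not mentioned.

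**The concern.** Safety is the only objective, and the study has one arm. The proportions of patients with an AE and with an SAE are the main result, and no comparator offsets events that precede exposure. As the shells stand, the report would show two AE proportions and two SAE proportions with none named as primary. The labels used in SAP 6.3.1, AEs and SAEs, match the unrestricted rows, which are the ones that break the protocol's rule.

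Table 14.2.1.2 raises a separate problem: a programmer cannot tell which events to count. It is the only summary table of treatment given, seriousness criteria and drug actions other than permanent discontinuation. Action taken with study drug has no clear meaning for an event that ended before the drug was given.

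**Working it through.** **1. Do the two rows of Table 14.2.1.1 include pre-dose events?** The footnote defines a TEAE as an AE after the first dose and sets no upper time limit. In dosed patients, the set of all AEs minus the set of TEAEs is then the set of AEs not after the first dose. If the any-AE row held no pre-dose events, it would equal the any-TEAE row and have no purpose. The same holds for the SAE pair. The rows therefore hold pre-dose events by construction, which the protocol excludes from summary tables.

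**2. What does Table 14.2.1.2 count?** Its footnotes define n as patients in the row category and E as the number of TEAEs. In Tables 14.2.1.3 to 14.2.1.10, n is the number of patients with a TEAE. Read literally, n in Table 14.2.1.2 covers any AE and E covers TEAEs only. It may equally be a TEAE table with a loose row label. The text does not decide between the two.

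**3. The plan's own figure.** The planning AE proportion is 31% with 10-point precision at 95% confidence (Protocol synopsis; SAP 4). n = 1.96² × 0.31 × 0.69 / 0.10² = 82.17, rounded up to 83, as stated. At 100 patients the half-width is 1.96 × √(0.31 × 0.69 / 100) = 9.1 points. Neither figure depends on this point.

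**4. Size of the excess.** Let p be the TEAE proportion and q the share of patients without a TEAE who had a pre-dose AE. The any-AE row reads p + q(1 − p), so the excess is q(1 − p). The documents give no q, so the values below are assumptions. The 31% is the planning value; 90% is an assumed high rate for contrast.

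| q (assumed) | Any-AE row, p = 31% | Excess (points) | Any-AE row, p = 90% | Excess (points) |
|---|---|---|---|---|
| 1% | 31.7% | 0.7 | 90.1% | 0.1 |
| 5% | 34.5% | 3.5 | 90.5% | 0.5 |
| 10% | 37.9% | 6.9 | 91.0% | 1.0 |

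For a rarer outcome such as SAEs, with p assumed to be 10%, q of 1% to 5% adds 0.9 to 4.5 points.

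**5. Which q is plausible?** The window is at most 7 days against about 230 days of observation: 7 / 237 = 3.0% of the total. If AEs occurred at a constant rate (an assumption), 31% over 141 to 230 days would imply q = 1 − 0.69^(7/141) = 1.8% down to 1 − 0.69^(7/230) = 1.1%. The excess would then be 0.69 × q = 1.3 down to 0.8 points. This suggests the lower end of the table, but it is an illustration and not an estimate.

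**The case against.** The strongest reply is that nothing is hidden. Table 14.2.1.1 prints the TEAE and serious TEAE proportions directly under the unrestricted rows, and its related, discontinuation and death rows are TEAE-only. Tables 14.2.1.3 to 14.2.1.10 are also TEAE-only and already cover seriousness, discontinuation, death, severity, relatedness and outcome. The SAP's precedence clause would let its tables govern. The schedule of activities shows no AE assessment at Visit 1, so few pre-dose events may be captured, although this sits uneasily with Protocol 8.2.2. The tables also cover dosed patients only.

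Most of this stands, and it limits the damage. It does not settle which row answers the primary objective or what Table 14.2.1.2 counts. A precedence clause is also no substitute for declaring a change that the SAP says it will detail.

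A reader might go further and infer that the main AE and SAE results are contaminated by chemoradiation after-effects. The documents do not support that:
- The SAP names no row as the main result.
- Protocol Appendix B 1 defines an AE as the development of an untoward occurrence, including deterioration of an existing one. Toxicity already present at entry is not thereby an AE; only what is new or worse between consent and dose 1 is added.
- Attributing those events to chemoradiation is inference. It is plausible because Protocol 5.2 excludes only unresolved toxicity above Grade 2 and pneumonitis of Grade 2 or more, but no figure is given.
- Restricting to TEAEs would not remove such effects. In the placebo-controlled study cited in Protocol 4.2, pneumonitis or radiation pneumonitis occurred in 24.8% of placebo patients, with a median onset of 55 days.

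**Conclusion.** The point holds as an undeclared conflict between documents and a gap in defining the primary estimate. Three things are established from the text alone: two rows of Table 14.2.1.1 contradict the protocol's rule on pre-treatment AEs; Table 14.2.1.2 contradicts itself on scope; and SAP 6.1.1 and 6.3.1 leave the primary AE and SAE proportions open between two candidates.

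The numerical effect is not established. It rests wholly on an assumed q and is probably small given the short window. The larger figures in the working need 5% to 10% of patients without a TEAE to have had a pre-dose AE, which nothing in the documents supports. Even 6.9 points would lie inside the planned half-width of 9.1 points at 100 patients. The case for change is that the result should be defined unambiguously in advance and that correcting it costs little.

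**What to change.** - **Table 14.2.1.1:** delete the any-AE and any-SAE rows. Do not relabel them as pre-treatment, because they hold both pre-dose and on-treatment events. Keep pre-dose AEs in the listings, as the protocol requires.
- **Table 14.2.1.2:** restrict it to TEAEs in title, row label and footnotes, with n and E on the same events.
- **SAP 6.3.1:** name the TEAE and serious TEAE proportions in the Safety Analysis Set as the primary estimates for AEs and SAEs.
- **TEAE footnote:** extend it to AEs that start before dose 1 and worsen after it. A worsening entered as a new event already qualifies, but one entered as a change to an existing record could be lost once pre-dose events are removed.

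If the sponsor prefers to keep the unrestricted rows, the SAP should declare the departure from the protocol and still name the TEAE rows as primary.

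The cost is minor shell and text edits. AE start and stop dates and times are already collected (Protocol 8.2.3; SAP Listing 16.3.1.2), and the sample size does not change. The reported AE percentage may differ slightly from the any-AE figure: lower without pre-dose events, with worsened events added back. Chemoradiation effects that first appear after dose 1 will remain in the TEAE counts.
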